11. **What is the primary purpose of the *Journal of Clinical Endocrinology and Metabolism*?**

The first step in the process of creating a new product is to identify the needs of the target market. This involves conducting market research to understand the wants and needs of potential customers. The research can be qualitative or quantitative, and it can be done through surveys, interviews, and focus groups. The goal is to gain a deep understanding of the target market's demographics, psychographics, and behavior patterns. This information is then used to develop a product that meets the needs of the target market.

[REDACTED]

[REDACTED]

[REDACTED]

[REDACTED]

[REDACTED]

[REDACTED]

3.3. Study Population

A potential subject will be included in the study if they meet the inclusion criteria described in the protocol. Subjects shall be 22 years of age or older, seeking treatment of moderate to severe tissue volume deficiencies in the infraorbital region with a grade of 2 to 3 (moderate to severe) on the TIOHS for both eyes.

If the subject meets any of the exclusion criteria, such as the exclusion of subjects with known hypersensitivity or previous allergic reaction to any component of the study device, or known history of multiple severe allergies, or history of anaphylactic shock, or any other criteria for exclusion, the subject is excluded from the study as per protocol.

Full list of inclusion/exclusion criteria is described in the protocol.

A total of 258 subjects (maximum 259) will be enrolled in the study, at least 20% subjects with Fitzpatrick skin types IV-VI (minimum 20% of the global study population) including at least 10% with Fitzpatrick skin types V/VI of which $\geq 3\%$ will have Fitzpatrick skin type V (≥ 8 subjects) and $\geq 3\%$ will have Fitzpatrick skin type VI (≥ 8 subjects).

[REDACTED]

[REDACTED]

[REDACTED]

[REDACTED]

[REDACTED]

[REDACTED]

[REDACTED]

[REDACTED]

[REDACTED]

3.4.1. Injection of Study Device

Method of administration will be either with a 30G ½" needle (included with the product) or a 25G 1½" cannula [REDACTED].

Injection area and depth: RHA [REDACTED] is injected from the sub-dermis to the periosteum in the infraorbital hollow.

Amount of filler to be administered: Up to 1.0 mL per eye at each treatment (max: 2.0 mL per treatment).

[REDACTED]

[REDACTED]

[REDACTED]

[REDACTED]

3.5. Method of Assigning Subjects to Treatment Groups

[REDACTED]

[REDACTED]

[REDACTED]

Randomization numbers will be assigned sequentially as subjects are entered into the study. The randomization will be stratified by site.

Needle and cannula subgroups are intended to be determined at the site level: the method of administration of RHA [REDACTED] (i.e., injection with a needle or a cannula) will be defined for each site

at the beginning of each stage of the study. The sites will be selected with an aim to achieve 1:1 distribution of subjects between the subgroups. [REDACTED]

[REDACTED]

[REDACTED]

[REDACTED]

[REDACTED]

If consent has been obtained, but the subject does not meet the entry criteria, they will be considered a screen failure and will not be enrolled.

3.6. Blinding and Unblinding

The TI, unblinded to allocation to groups, will be asked to minimize the number of people who will have the allocation information or who will have any form of access to such information.

[REDACTED]

[REDACTED]

The BLE and study personnel not involved with the site (e.g., data management, medical monitor) will be blinded to assignment to groups and, if possible, to subgroups.

[REDACTED]

[REDACTED]

Subjects will not be blinded.

Unblinding in case of medical emergency is not applicable since the TI, who is in charge of safety follow-up of subjects, will be aware of the treatment administered.

Overall unblinding will take place at the end of the study only after database lock has occurred.

[REDACTED]

[REDACTED]

4. Statistical Analysis and Reporting

4.1. Introduction

Data processing, tabulation of descriptive statistics, calculation of inferential statistics, and graphical representations will be performed primarily using Statistical Analysis Software (SAS) release 9.4 or higher. If the use of other software is warranted, the final statistical methodology report will detail what software was used for what purposes.

Continuous (quantitative) variable summaries will include the number of subjects (n) with non-missing values, the number of missing values, mean, 95% confidence interval (CI) (as applicable), SD, median, minimum, and maximum, unless otherwise specified.

Categorical (qualitative) variable summaries will include the frequency and proportion of subjects who are in a particular category, or for each possible value.

For non-visit based data point proportions (AEs, CTRs, medications), the denominator for the percentage calculation will be based upon the total number of subjects in the study population. For visit based data point proportions, like response rates and categorical proportions at visits, calculation will be based upon the total number of subjects with non-missing data for the observation at the specific visit.

95% CIs of proportions will be also presented where indicated in this SAP.

The number of missing values will be calculated as difference of the total number of values in the study population minus the number of non-missing values.

The minimum and maximum will be reported with the same degree of precision (i.e., the same number of decimal places) as the observed data. Measures of location (mean and median), and CI will be reported to 1 more decimal place than the observed data, and SD will be reported to 2 more decimal places than the observed data.

Percentages will be presented to 1 decimal place, unless otherwise specified.

[REDACTED]

[REDACTED]

[REDACTED]

A black and white image showing a series of horizontal black bars of varying lengths and positions, suggesting a heavily redacted document. The bars are irregular in shape, with some being solid horizontal lines and others having irregular, stepped edges. They are positioned at different heights and widths across the frame, creating a sense of fragmentation and obscuring any original content.

4.2.3. Data Monitoring Committee

Not applicable.

5. Analysis Populations

The following 4 analysis populations are planned for this investigation:

- **Screening population:** All subjects who provide informed consent and demographic and/or Baseline Screening assessment results, regardless of their randomization and treatment status in the investigation. The untreated control group will only be included in the Screening population as they will not receive RHA█ treatment throughout the clinical study.
- **Safety population (SAFT):** All subjects who are assigned to either the RHA█ group or the No-treatment control group and complete Visit 1 █. Subjects will be

analyzed according to their actual arm received.

- **Intent-to-Treat population (ITT):** All subjects who are randomly assigned to either the RHA [REDACTED] or the No-treatment control group and complete Visit 1. Subjects will be analyzed according to their initial arm assignment regardless of whether or not they received RHA [REDACTED].
- **Per Protocol population (PP):** All subjects in the ITT population who completed up to Visit 5 (primary endpoint visit at 12 weeks) with no major CIP deviations that could affect effectiveness assessments. The sponsor will identify major CIP deviations per Protocol Deviation Guidance Plan (PDGP) prior to the database lock.

[REDACTED]

[REDACTED]

[REDACTED]

[REDACTED]

[REDACTED]

[REDACTED]

6. General Issues for Statistical Analysis

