2.2.2. Safety Endpoints

The safety endpoints of this study include the following:

- Adverse events (AEs), with a focus on treatment related AEs based on the TI assessment, and AEs reported from the Common Treatment Response (CTR) diary, from randomization

Post-injection CTR,

Each AE will be coded to a Preferred Term (PT) and associated System Organ Class (SOC) according to an established and validated adverse reaction dictionary (Medical Dictionary for Regulatory Activities [MedDRA], latest available version) before the randomized treatment code is broken.

3. Overall Study Design and Plan

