Phase 1a: Up to 12 weeks after the initial treatment for the RHA█ group or after randomization for the No-treatment control group; primary endpoint

Subjects who will be randomly assigned to the RHA [REDACTED] group at Screening [REDACTED] [REDACTED] will receive their injection at Visit 1. The TI or designee will call subjects 72 hours post-treatment (Visit 1 Call). Subjects will come to the site [REDACTED] [REDACTED] 12 weeks (Visit 5, primary endpoint) after the initial treatment. Afterwards, subjects will proceed directly to Phase 2. Phase 1b is not applicable for subjects randomly assigned to the RHA [REDACTED] group.

Subjects randomly assigned to the No-treatment control group at Screening will receive

no treatment in Phase 1a of the study. They will come to the site [REDACTED] [REDACTED] 12 weeks (Visit 5, primary endpoint) after randomization. After completing all assessments for Visit 5, subjects will immediately begin Phase 1b (Visit 1b is on the same day as Visit 5) and will receive their initial treatment with RHA [REDACTED].

[REDACTED]

Phase 1b: after the primary endpoint assessment up to 12 weeks after the initial treatment for the No-treatment control group

Phase 1b is only applicable to subjects initially randomly assigned to the No-treatment control group. Once all evaluations applicable for Visit 5 are completed, subjects will proceed directly to Visit 1b (on the same day). Evaluations completed at Visit 5 will be used for Visit 1b and will become the new Baseline for Phase 1b.

Subjects will receive their initial treatment with RHA [REDACTED] at Visit 1b.

Subjects will follow the same schedule as those initially randomly assigned to the RHA® 1 group: RHA® 1 will be administered on the same day (Visit 1b). The TI or designee will call the subject 72 hours post-treatment (Visit 1b Call). Subjects will come to the site [REDACTED] [REDACTED] 12 weeks (Visit 5b) after their initial treatment. Afterwards, subjects will proceed to Phase 2.

Phase 2 and Exit visit: 12 weeks after the initial treatment up to the end of the study for the RHA [REDACTED] group and the No-treatment control group

Phase 2 will occur 12 weeks after receiving initial treatment with RHA [REDACTED] for subjects in the RHA [REDACTED] and the No-treatment control group (after Phase 1b).

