7.4. Exposure and Compliance

Data will be tabulated for Safety population.

Number of treatment sessions will be tabulated in a frequency table for RHA [REDACTED] and No-treatment control groups.

[REDACTED]

[REDACTED]

Number of device malfunction reported by visit will be tabulated in a frequency table by treatment group.

All exposure data will be listed.

8. Effectiveness Analysis

All effectiveness analysis will be based on the ITT population. Primary endpoint and TIOHS responder as assessed by BLE analyses will be repeated for the PP population.

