8.3.5. Subject Satisfaction Score

Subject Satisfaction will be assessed by subjects using the following static 5-grade scale.

Grade description:

1. Very satisfied
2. Satisfied
3. Neither satisfied nor dissatisfied
4. Dissatisfied
5. Very dissatisfied.

Satisfaction grade frequencies and percentages will be calculated and presented for each scheduled study visit.

For subject satisfaction, proportions of “satisfied” and “very satisfied” (subject satisfaction responder rate) will be presented, along with the 95% CI of the proportion at each applicable study visit. Fisher’s exact test will be performed to compare responder rates at each applicable visit.

A series of 15 horizontal black bars of varying lengths, arranged vertically. The lengths of the bars decrease from top to bottom, creating a descending staircase effect. The bars are set against a white background.

9. Safety and Tolerability Analysis

All safety analyses will be performed on the Safety population.

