9.1. Adverse Events

All AEs will be coded using the MedDRA dictionary.

Number of all AEs, ADEs, [REDACTED] and number and percentage of subjects having the specific AEs will be presented. 2-sided exact 95% CIs will be calculated for the proportion of subjects having the specific AEs.

All AEs reported during the study will be described by SOC and PT.

Incidence rates defined as number of subjects presenting the AE divided by the number of subjects in the treatment group with 2-sided exact 95% CIs will be calculated for the overall incidence of AEs, ADEs, [REDACTED]

The causal relationship of the AE to the study treatment is determined by the investigator by relationship to the study procedure and relationship to the study device [REDACTED]

[REDACTED]

[REDACTED]

[REDACTED]

[REDACTED]

[REDACTED]

[REDACTED]

[REDACTED]

[REDACTED]

A document page with several large black rectangular redactions covering the majority of the text area. The redactions are irregular in shape, suggesting redacted content.

Individual listings of all AE data will also be given.

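### As visibly worded, the Safety population requires completion of Visit 1 rather than exposure, so an injected subject who does not finish that visit could be missing from the safety and exposure tables

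*SAP*

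**What the plan says.** SAP section 5 (Analysis Populations) sets two conditions for the Safety population: assignment to an arm, and completion of Visit 1. The text reads: RHA "group or the No-treatment control group and complete Visit 1". A short redaction follows directly. Members are then "analyzed according to their actual arm received".

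Section 3.1 places the first injection inside that visit: subjects randomised to RHA "will receive their injection at Visit 1".

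Three sections rely on the population:
- Section 9: "All safety analyses will be performed on the Safety population".
- Section 7.4, on exposure: "Data will be tabulated for Safety population".
- Section 4.1, for adverse events, common treatment responses and medications: "the denominator for the percentage calculation will be based upon the total number of subjects in the study population".

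Two sections describe a wider scope for adverse events. Section 2.2.2 includes "AEs reported from the Common Treatment Response (CTR) diary, from randomization", and section 9.1 states "All AEs reported during the study will be described by SOC and PT".

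**The concern.** A safety population normally consists of everyone exposed. Here the visible entry rule does not mention receipt of the device; it asks whether the visit in which the device is injected was completed. An RHA subject injected in one or both eyes who does not finish Visit 1 is exposed but does not meet the rule as visibly written.

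The reason for not finishing may be connected with the injection. If it is, the exclusion depends on outcome, and it removes the subject from both the numerator and the denominator of the incidence rates. Section 1.1 says that no soft tissue filler is FDA-approved for this region, that existing data come from retrospective studies and case reports, and that the trial is to support a US marketing application. The tabulated rate of uncommon acute events is therefore an output that readers will look at closely.

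**Working it through.** The SAP gives no figure that depends on this definition, so there is nothing of its own to reproduce. The check compares the sections and then adds an illustration.

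**Step 1. Order of events at Visit 1.** Under section 3.1, screening, randomisation and (in the RHA arm) injection all belong to Visit 1. Exposure therefore comes before completion, and being exposed without completing is possible. The gap concerns subjects randomised to RHA. Controls are first injected at Visit 1b, on the day of Visit 5, long after their own Visit 1.

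**Step 2. Does another population include the subject?** The ITT definition in section 5 carries the same completion condition, and the PP population is a subset of the ITT. Only the Screening population is left, and section 9 does not use it for safety.

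**Step 3. What is lost and what is kept.** The subject would leave the exposure tables (7.4), the adverse event and common treatment response tables (9.1, 9.2) and their denominators (4.1). The subject would stay in the listings: section 6.1.7 lists all collected data, section 9.1 lists adverse events by individual, and section 9.1.1 lists deaths.

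**Step 4. Consistency.** An event after randomisation but before the end of Visit 1 falls within the scope of sections 2.2.2 and 9.1. The entry rule in section 5 could keep it out of the tables that are meant to deliver that scope. Section 5 also assigns members to arms by what they received, which is an exposure principle, while admitting them by visit completion.

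**Step 5. Illustration.** Planned enrolment is 258, at most 259 (section 3.3), with 3:1 allocation (section 3.1). RHA arm: 258 × 3/4 = 193.5, and 259 × 3/4 = 194.25, so about 194. Section 9.1 specifies two-sided exact 95% intervals. For x events in n subjects the Clopper-Pearson limits are:
- lower = the 0.025 quantile of Beta(x, n − x + 1), or 0 when x = 0;
- upper = the 0.975 quantile of Beta(x + 1, n − x), which for x = 0 equals 1 − 0.025^(1/n).

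Suppose that k injected subjects each have an acute event, that none of them completes Visit 1, and that no other subject has that event. The SAP gives no value for k.

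| k | All exposed counted | Visible rule |
|---|---|---|
| 1 | 1/194 = 0.5% (0.01% to 2.8%) | 0/193 = 0% (0% to 1.9%) |
| 2 | 2/194 = 1.0% (0.1% to 3.7%) | 0/192 = 0% (0% to 1.9%) |
| 3 | 3/194 = 1.5% (0.3% to 4.5%) | 0/191 = 0% (0% to 1.9%) |

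For k = 1 under the visible rule: 1 − 0.025^(1/193) = 0.0189. With k = 0 nothing changes.

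**The case against.** The strongest objection is that the decisive words may be hidden. The Safety definition has a redaction immediately after the completion condition, and the otherwise parallel ITT definition has none there. More redacted lines follow in section 5. Any of this could qualify the condition. The visible text also does not define completion, which a protocol may well do. If it means only that the Visit 1 injection was given, the gap closes.

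A reader might infer something stronger: that a subject who reacts acutely to the injection is withdrawn during Visit 1 and so disappears from the safety report. The SAP does not support that. Nothing visible says that an acute reaction ends Visit 1 early or causes it to be recorded as incomplete. The document points towards continued observation: a call at 72 hours and follow-up of ongoing adverse device effects (section 3.1), and end-of-study assessments for those who discontinue (section 6.1.3.1). The event would also still appear in the listings.

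These arguments limit the point without removing it. The visible criterion is completion and not exposure, and no visible text admits an injected subject who does not complete the visit. Listings do not supply the incidence rates and exact intervals that section 9.1 promises. If the intended meaning is that injection suffices, stating it takes the same one-sentence edit.

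**Conclusion.** The point holds as a low-severity defect in a definition. As visibly worded, Safety membership depends on finishing the visit in which the device is injected. The consequence is conditional on three assumptions: that the redacted text does not change the condition, that the protocol does not define completion so as to cover every injected subject, and that at least one injected subject fails to finish Visit 1. If all three hold, the safety and exposure tables omit an exposed subject, possibly for a reason related to an acute event.

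The number affected cannot be estimated from the document. It is probably very small and may be zero. The shift from 1/194 to 0/193 shows what a single case with an event would do; it does not predict that one will occur. No primary analysis or success criterion depends on this definition.

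**What to change.** In SAP section 5, remove the Visit 1 completion condition from the Safety population and define membership by exposure. Suggested wording: *All subjects who received any amount of RHA, in either eye and at any visit, together with all subjects randomised to the No-treatment control group for their untreated period; subjects are analysed by the arm actually received.*

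If the redacted text or the protocol already has this effect, the new sentence only makes it explicit. The edit should be made before database lock, so that nobody has to decide case by case, knowing the event, whether an injected subject completed the visit.

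The cost is one sentence in the SAP and the matching population flag in the programs. It needs no new data, visits or subjects, and it changes no treatment rule.

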3.1. Overall Design

Enrollment:

This is a multicenter, blinded evaluator, randomized, prospective, no treatment control clinical study to identify whether RHA [REDACTED] is superior to no treatment for the correction of moderate to severe tissue volume deficiencies in the infraorbital regions. The study [REDACTED] [REDACTED] will include at least 20% of subjects with Fitzpatrick skin types IV-VI: including minimum of 10% subjects presenting with Fitzpatrick skin types V or VI of which $\geq 3\%$ will have Fitzpatrick skin type V [REDACTED] and $\geq 3\%$ will have Fitzpatrick skin type VI [REDACTED].

The TI and the BLE will evaluate the subject's infraorbital hollows independently of each other using the TIOHS at Screening (Visit 1) for eligibility. If the assessments of the TI and the BLE are the same or differ exactly by 1 point on the scale, the difference will be considered acceptable. The TI and the BLE must agree that the subject meets the inclusion criterion number 4 (TIOHS grade 2 or 3). Bilateral symmetry is not required. If the subject is eligible, the BLE's assessment will be used for the Baseline of the primary endpoint. If the TI and the BLE do not agree on eligibility, or if their assessments differ by 2 points or more on the scale, the subject will not be eligible.

A black and white image showing a series of horizontal black bars of varying lengths, suggesting a redacted document. The bars are positioned in a descending staircase pattern from top to bottom. The top bar is the longest, followed by a shorter one, then a very long one, then a medium one, then a short one, and finally a very long one at the bottom. The background is white.

Subjects enrolled will be randomly assigned in a ratio of 3:1 at Screening (Visit 1) to receive RHA [REDACTED] or to receive no treatment (No-treatment control group). Subjects receiving RHA [REDACTED] will be further divided by the method of administration (i.e., injection with a needle or a cannula), which will be defined for each site before the beginning of the study. Depending on the site, RHA [REDACTED] will be administered with a 30G ½" needle [REDACTED] or with a 25G 1 ½" cannula [REDACTED]. Site selection will aim to achieve approximately 1:1 distribution between the subgroups. The BLE will be blinded to the study groups (RHA [REDACTED] group or No-treatment control group).

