8.1. Primary Effectiveness Analysis

Primary endpoint:

Primary endpoint is the responder rate after 12 weeks.

A responder is defined as a subject with an absolute ≥ 1 -grade improvement in both eyes on the TIOHS as assessed by the BLE from before initial treatment to 12 weeks after the initial treatment (Visit 5). A negative change from Baseline value is considered as an improvement. Subject with missing assessment for at least one eye at Visit 5 will be considered as a non-responder.

Responder rate at Visit 5 as assessed by the BLE will be tabulated by treatment group: frequency of responders, percentage of responders along with 95% CI will be tabulated. Fisher's exact test will be performed to compare responder rates between RHA [REDACTED] and the No-treatment control group. Test will be one-sided with a Type I error rate at 0.025. To achieve superiority, the observed P value must be ≤ 0.025 .

[REDACTED]

Missing data will be handled as described in section 6.1.3.1.

Additionally, the following 2 conditions must be met:

- At least 70% of the subjects treated with RHA [REDACTED] must be responders
- The difference between the responder rate for subjects treated with RHA [REDACTED] and the No-treatment control group must be $\geq 50\%$ points.

Co-primary endpoint:

The co-primary endpoint will be the change from Baseline in the modified FACE-Q "Appraisal of lower eyelids" domain score [REDACTED]

[REDACTED] and the average change from Baseline of the modified FACE-Q "Appraisal of lower eyelids" converted raw score at 12 weeks. Missing data will be handled as described in section 6.1.3.1.

[REDACTED]

Superiority will be declared if:

- the lower bound of 2-sided 95% confidence interval for the responder rate for RHA [REDACTED] is at least 70%, and
- the lower bound of 2-sided 95% confidence interval for the difference in the responder rate between subjects treated with RHA [REDACTED] and the No-treatment control group is at least 50%, and
- the lower bound of 2-sided 95% confidence interval for the modified FACE-Q “Appraisal of lower eyelids” raw score for RHA [REDACTED] is at least 3, and
- the lower bound of 2-sided 95% confidence interval for the difference in mean change from Baseline of the modified FACE-Q between RHA [REDACTED] treated group and the No-treatment control group is at least 12.

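### The ITT set is conditional on completing Visit 1, the visit at which subjects are randomised, so a randomised subject who leaves mid-visit drops out of every effectiveness analysis

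*SAP*

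**What the plan says.** Five parts of the SAP bear on this point.

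- **Randomisation (Section 3.1, Enrollment).** "Subjects enrolled will be randomly assigned in a ratio of 3:1 at Screening (Visit 1) to receive RHA" or no treatment.
- **Rest of Visit 1 (Section 3.1, Phase 1a).** Subjects allocated to RHA "will receive their injection at Visit 1". Controls receive "no treatment in Phase 1a of the study".
- **Blinding (Section 3.6).** "Subjects will not be blinded". The treating investigator also knows the allocation.
- **ITT definition (Section 5).** Subjects must be randomised and must "complete Visit 1. Subjects will be analyzed according to their initial arm assignment regardless of whether or not they received RHA". The per-protocol set is drawn from the ITT set.
- **Use of the set (opening of Section 8).** "All effectiveness analysis will be based on the ITT population".

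Two rules deal with a missing Visit 5 grade on the Teoxane Infraorbital Hollows Scale (TIOHS). Section 6.1.3.1 prescribes multiple imputation under missing-at-random, explicitly for subjects in the ITT set. Section 8.1 counts a subject with a missing eye at Visit 5 as a non-responder, and also refers back to Section 6.1.3.1.

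**The concern.** An ITT set should be fixed by randomisation alone. Here membership also depends on something that happens afterwards, in subjects who already know their allocation, at a visit whose remaining content is scheduled differently in the two arms. An RHA subject may decline or break off the injection. A control may leave on learning that no treatment will be given for 12 weeks. If either departure means that Visit 1 is not completed, the subject disappears from the primary analysis, the secondary analyses and the per-protocol repeat alike.

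The missing-data rules cannot bring such a subject back. Imputation is confined to ITT members, and the non-responder rule operates inside an analysis that is itself restricted to the ITT set. Exclusion is also unnecessary: the blinded evaluator grades the TIOHS at Visit 1 for eligibility, and that grade is the baseline for the primary endpoint, so a randomised subject should already have one.

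The primary claim is at stake. Section 8.1 asks for a lower 95% confidence bound of at least 70% for the RHA responder rate and at least 50% for the difference. Fixed thresholds of this kind are sensitive to the denominator when a result lies close to them.

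**Working it through.** The SAP attaches no figure to the definition, and its readable text gives no assumed rates, power or dropout. There is nothing to reproduce, so what follows is a sensitivity calculation.

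**Inputs from the SAP**
- "A total of 258 subjects (maximum 259) will be enrolled in the study" (Section 3.3).
- Allocation 3:1 (Section 3.1): 258 × 0.75 = 193.5, taken as 194 RHA, leaving 64 controls.
- Thresholds of 70% and 50% for the lower 95% bounds (Section 8.1).

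**Assumptions**
- The number k of randomised RHA subjects who do not complete Visit 1 is not given. It is varied from 0 to 19.
- The interval methods for the responder rate and for the difference are not visible in the readable text. Clopper-Pearson is used for the rate and Newcombe for the difference.
- Restored subjects count as non-responders (the Section 8.1 rule).

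**Step 1: the 70% criterion near the boundary.** The lower bound is the 2.5th percentile of Beta(x, n − x + 1), with x responders among n subjects.

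| Responders / n | Rate | Lower bound | At least 70%? |
|---|---|---|---|
| 149/194 | 76.8% | 70.2% | yes |
| 148/194 | 76.3% | 69.7% | no |
| 148/193 (k = 1) | 76.7% | 70.1% | yes |
| 148/192 (k = 2) | 77.1% | 70.5% | yes |

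With 148 responders, one excluded subject settles the criterion. A Wilson interval behaves in the same way: 69.8% for 148/194 and 70.2% for 148/193.

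**Step 2: the same criterion away from the boundary.** With all 194 in the denominator, at least 149 responders are needed.
- Observed rate 80%: with k = 6, 150/188 (bound 73.3%) becomes 150/194 (70.8%) and still passes. With k = 9, 0.80 × 185 = 148 responders, and 148/194 fails. With k = 10, 147/184 (73.4%) becomes 147/194 (69.1%) and fails.
- Observed rate about 90%: with k = 19, 158/175 (84.9%) becomes 158/194 (75.2%) and passes comfortably.

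**Step 3: how likely a reversal is when k = 2.** Among the 192 retained subjects, 147 responders already fail (69.9%) and 149 pass even with 194 in the denominator. Only exactly 148 responders reverses the result. The binomial probability of 148 in 192 is about 4% at a true rate of 80% and about 0.1% at 85%.

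**Step 4: the 50% difference.** The Newcombe lower bound is d − √[(p₁ − l₁)² + (u₂ − p₂)²], where l₁ and u₂ are the Wilson lower limit for RHA and upper limit for control. With an assumed 10/64 control responders, 150/188 in the RHA arm gives 51.7%. Restoring six RHA subjects (150/194) gives 49.1%.

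Losses among controls work the other way. If six controls who would count as non-responders are dropped, the control rate goes from 10/64 = 15.6% to 10/58 = 17.2%, which narrows the difference.

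**The case against.** A reader might infer that completing Visit 1 means having been injected in the RHA arm and only having been assessed in the control arm, so that the exclusion is arm-dependent by construction and the ITT definition contradicts itself. The SAP does not support that. Section 3.1 schedules the injection at Visit 1 but does not make it part of completing the visit. The Section 5 wording that keeps subjects whether or not they received RHA has content only if an uninjected RHA subject can belong to the set, so the natural reading is that completion does not require injection. Text is also blacked out around the population definitions and in the randomisation section, and the protocol is not shown, so a definition of completion may exist elsewhere. Neither arm-dependence nor an internal conflict is established.

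The size is also open to challenge. Randomisation and injection share one visit, which leaves a short window for loss. The borderline figures need an assumed number of non-completers, an assumed interval and the less favourable of two missing-data rules. Under the imputation in Section 6.1.3.1, whose model includes treatment group, restored RHA subjects would resemble other RHA subjects and the rate would barely move. Departing controls are dropped as well, and on the non-responder rule that makes the difference conservative.

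All of this limits size and direction, and it stands. It does not answer the remaining point: under the readable definition, a subject who leaves after allocation and before the visit ends is outside the set, whatever completion is later taken to mean.

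**Conclusion.** The point holds as a defect of definition. The ITT set carries a post-randomisation condition, left undefined in the readable text, in a trial where subjects know their arm, and no missing-data rule reaches those it removes. The exclusion may differ by arm, but this is not shown. Bias is a risk, not a demonstrated effect, and its direction on the between-arm difference is not fixed.

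On the single-arm 70% criterion, dropping RHA subjects who would otherwise be non-responders can only raise the bound. The practical effect ranges from decisive on one or two exclusions in a borderline result, through nine exclusions at an observed 80%, to none with 19 exclusions at about 90%. These figures rest on 194 RHA subjects, an exact interval and the non-responder rule. With multiple imputation the shift would be small.

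The change should be made because it is cheap and settles the set before unblinding. The figures do not show that the primary conclusion is in danger.

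**What to change.** 1. In SAP Section 5, delete the Visit 1 completion condition from the ITT definition, so that the set is all subjects randomised to RHA or to the No-treatment control group, analysed as randomised.
2. Reconcile Section 6.1.3.1 (multiple imputation) with Section 8.1 (non-responder), and apply the one resulting rule to every randomised subject without Visit 5 data. Without this step, the first change does not determine how the restored subjects enter the responder rate.
3. Add to the disposition table in Section 7.1 the number of randomised subjects, by arm, who did not complete Visit 1.

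The cost is one sentence in the definition, one clarified rule and one table row. The downside is possibly a few more subjects with missing Visit 5 data and, if the non-responder rule is kept, a slightly lower responder rate.
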